6 STUDY AGENT

6.1 STUDY AGENT(S) AND CONTROL DESCRIPTION

6.1.1 ACQUISITION

Both Climara patches (transdermal E2) and Prometrium pills (oral micronized P4) will be acquired through UIC Investigational Drug Services from their respective manufacturers.

IDS will order climara + prometrium as well as appropriate placebo materials.

6.1.2 FORMULATION, APPEARANCE, PACKAGING, AND LABELING

Please see attached inserts for information about active Climara patches (transdermal E2) and Prometrium (oral micronized P4). Both transdermal E2 and oral micronized P4 are readily commercially available. Placebo patches and pills (both in stock at UIC IDS) are formulated and designed to be identical in appearance to these agents; all packaging and blinding will be accomplished via UIC Investigational Drug Services.

6.1.3 PRODUCT STORAGE AND STABILITY

Both Climara and Prometrium can be stored at room temperature for the duration of an individual's study participation. Participants will be instructed to avoid exposing study drugs to extreme temperatures or humidity. More specific information about storage and stability can also be found in the attached inserts for Climara and Prometrium.

6.1.4 PREPARATION

All preparation will be handled by UIC Investigational Drug Services (IDS), who will blind and mask the study drugs. No further preparation will be required by study staff or participants.

6.1.5 DOSING AND ADMINISTRATION

Dosages of E2 and P4 will be fixed. Dosages will not be tied to meals, but will be 12 hours apart in the morning and evening.

6.1.6 ROUTE OF ADMINISTRATION

E2 will be administered via transdermal patch. Micronized P4 will be administered orally in pill form.

6.1.7 STARTING DOSE AND DOSE ESCALATION SCHEDULE

In the experimental conditions of the study, the dosages will be fixed and not changed.

6.1.8 DOSE ADJUSTMENTS/MODIFICATIONS/DELAYS

If the PI determines that a participant must be discontinued from the protocol (see Section 5.4.2), The PI and [name] will be unblinded via IDS. If the participant was on active E2/P4, [name] will supervise the subject's discontinuation of E2/P4. Regardless of the condition the participant was in, the PI and [name] will continue to follow the participant until resolution via appropriate clinical care (e.g., hospitalization for suicidality).

6.1.9 DURATION OF THERAPY

The planned duration of active treatment is 14 days. All days in which participants use patches and pills will be utilized in multilevel modeling analyses, which accommodate unbalanced/missing data.

6.1.10 TRACKING OF DOSE

For patches (E2): E2 patches will be applied (day +7 following ovulation) and changed (day +14 following ovulation) in the laboratory; therefore, no compliance issues are anticipated for E2. One extra patch will be given to each participant in the case that the patch falls off. All used patches will be brought to the lab so that use of patches can be monitored.

For pills (P4): at the first lab visit, study staff will work with participants to develop individualized methods for reminding the participant to take twice-daily study pills, including but not limited to email reminders, phone call reminders, text reminders, app-based reminders (with data stored locally only), pill charts, calendar reminders, and stimulus control (e.g., putting study medication on bedside table. Participants will bring in pill bottles to each visit so compliance can be monitored.

6.1.11 DEVICE SPECIFIC CONSIDERATIONS

Not applicable.

CLEAR 2 Study Protocol: Hormones and Suicide Risk, Version 9, 07-02-2020, Page 28 of 64

6.2 STUDY AGENT ACCOUNTABILITY PROCEDURES

Research staff pick up agents from IDS and distribute to subjects as outlined in the study schedule below. All unused pills and patches will be returned to study staff, who will return them to IDS. IDS will dispose of unused materials according to regulations.

7 STUDY PROCEDURES AND SCHEDULE

7.1 STUDY PROCEDURES/EVALUATIONS

7.1.1 STUDY SPECIFIC PROCEDURES

PHONE SCREENING

Variable	Interview Measure	Self-Report Measure	Task Measure
Inclusion/Exclusion Criteria	Х	-	-
Psychiatric Diagnosis	Self- reported Previous Diagnosis	-	-
Suicidality	Abbreviated SITBI	-	-

ENROLLMENT VISIT – 1 VISIT @ 4 HRS

- **Timing:** Can occur at any time provided that it allows for the participant to complete the protocol in the term of IRB approval.
- Assessments Administered (see section 4.1 for Abbreviations):

Variable	Interview Measure	Self-Report Measure	Task Measure
Vitals	-	Height/Weight	-
Inclusion/Exclusion Criteria	х		
Psychiatric Diagnosis	SCID	-	-
Suicidality	Full SITBI	-	-
Depression	-	CESD	-
Hopelessness	-	BHI	-
Inhibitory Control	-	UPPS-P	-
Threat Sensitivity	-	STAI	-
Negative Social Appraisals	-	SSES	-

LABORATORY TESTING VISITS – 9 [contact] HRS

• **Timing:** The nine laboratory visits for each condition will occur on days +7, +14, and +22 following positive ovulation test (day 0) in each condition. The

CLEAR 2 Study Protocol: Hormones and Suicide Risk, Version 9, 07-02-2020, Page 29 of 64

acceptable windows will be +/- 2 days in either direction for each visit.

Variable	Interview Measure	Self-Report Measure	Task Measure
Urine Pregnancy Screen	-	-	x
(1 st lab visit of each condition)			
Urine Drug Testing	Х	Х	х
Vitals (1 st lab visit of each condition)	-	-	Height/Weight
Blood Sample (48 ml)	-	-	E2/P4/ALLO/Inflammatory Gene Expression
Suicidality	Full SITBI	-	-
Depression	-	CESD	-
Hopelessness	-	BHI	FT-IRAP
Inhibitory Control	-	UPPS-P	SST
Threat Sensitivity	-	STAI	DPT
Negative Social Appraisals	-	SSES	SAR-IAT
Side Effects and	Х	-	-
Compliance Monitoring			
Parasympathetic Activity	-	-	Respiratory Sinus Arrhythmia

• Assessments Administered (see section 4.1 for Abbreviations):

DEBRIEFING VISIT – 1 HOUR

- **Timing:** Debriefing will occur within a 15 day window following completion of the second condition.
- Individual results will not be reported to the patient.
- Referral to original care provider will be facilitated as necessary.
- Assessments Administered (see section 4.1 for Abbreviations):

Variable	Interview Measure	Self-Report Measure	Task Measure
Final Suicide Risk Assessment	Full SITBI	-	-

7.1.2 STANDARD OF CARE STUDY PROCEDURES

Although the LRAP/UWRAP dictates the provision of basic supportive conversation and other simple interventions to reduce imminent risk in the context of increased suicidality, participants are expected to utilize their mental health provider for any treatment needs that arise during the course of the study.

7.2 LABORATORY PROCEDURES/EVALUATIONS

7.2.1 CLINICAL LABORATORY EVALUATIONS

A point-of-care urine **pregnancy test** will be completed in our laboratory on site at the first visit of all three conditions. A positive pregnancy test will result in termination of participation and will be managed by [name].

At the beginning of each experimental condition, we will also collect a urine sample and perform rapid urine toxicology screens for cocaine, opioids, cannabis, and methamphetamine on-site through the CRC nursing staff using Ten Panel Integrated EZ Split Key Drug Test Cup with temperature-sensitive strips. A positive result for cocaine, opioids, or methamphetamine will result in exclusion. THC use will be allowed as long as the participant does not meet criteria for a substance use disorder on the SCID-I.

At all 9 laboratory assessments during active treatment with placebo or E2/P4, participants will provide 48ml of blood to be assayed for E2/P4, ALLO, and inflammatory gene expression, to evaluate the success of the hormone in achieving stable luteal phase levels of E2/P4/ALLO, as well as more stable inflammatory markers. Storage onsite will be handled by the CTSA CRC staff.

7.2.2 OTHER ASSAY PROCEDURES

Gene Expression Measurement and Coding. Total RNA will be extracted using a Qiacube automated nucleic acid preparation system (Qiagen, Valencia, CA). Resulting RNA samples will be tested for suitable mass (Nanodrop ND1000) and integrity (Agilent Bioanalyzer), and converted to fluorescent cRNA for hybridization to human HT-12 BeadChips (Illumina, San Diego, CA). Expression values for all human gene transcripts will be determined, with individual samples subject to quantile normalization and log2-transformation to stabilize variance for linear model-based analyses of differential gene expression and subsequent interpretive bioinformatics.

Genomic data will be included in analyses using composite measures of *a priori*-defined gene sets involved in inflammation, Type I interferon-related antiviral responses, and antibody production. From a specific set of 53 genes, we will form composites of 19 pro-inflammatory genes, 31 Type I interferon-related genes, and 3 antibody-related genes. Composites will be formed by averaging standardized values of each (log2-transformed, quantile normalized) gene transcript. Cronbach's alpha reliability coefficients for such transcript composites are typically in excess of .80, and we expect similarly reliable composites in this study. In addition, we will complete a "bottom-up" analysis of all sets of genes that are systemically up- or down-regulated across the perimenstrual weeks as a result of our experimental conditions (E2, P4) relative to placebo.

7.2.3 SPECIMEN PREPARATION, HANDLING, AND STORAGE

48 ml of blood will be collected using: (1) one 20-ml red-top tube (no additive), (2) one 20-ml lavender-top tube (EDTA additive), and (3) one 8-ml PaxGene RNA tube. 20ml of blood (red-top tube) will be centrifuged and serum will be aliquoted into storage tubes and stored in a -80F freezer in the Clinical Research Center. These will be transported to the core laboratory in batches for estrogen and progesterone assay. Following assay, any additional serum will be stored by the CRC. The other 20 ml tube of blood (lavender-top tube) will be transferred to [name] laboratory within 48 hours of the draw, and will be centrifuged and separated into plasma aliquots (for measurement of GABAergic neurosteroids using GC-MS) and

lymphocyte aliquots (for use in gene expression assays related to neurosteroid synthesis and function), then stored in a -80 F freezer in the [name]. Standard freezer-proof labels will indicate participant ID and study session. A PaxGene RNA blood tube will be utilized to collect an additional 8ml of blood for use in gene expression assays related to inflammation. Following analysis, the PaxGene RNA blood samples will also be destroyed.

7.2.4 SPECIMEN SHIPMENT

Serum transport will be handled by Clinical Research Center staff. Serum samples will analyzed in batches when there are enough aliquots to support purchase of RIA kits. Lavender top tubes will be transported to Dr.[name]'s lab by CLEAR Lab staff members. PaxGene tubes will be stored until assay at the conclusion of the experiment, and will be analyzed in a single batch.

7.3 STUDY SCHEDULE

7.3.1 SCREENING

The screening procedures described below must take place prior to the enrollment visit; because all information about eligibility obtained during the phone screen is confirmed at the enrollment visit, there is no expiration of screening procedures after which they must be repeated.

Following verbal consent, verbal phone screening will include verbal assessment of all inclusion/exclusion criteria described above, including assessment of recent suicidality using the shortened SITBI.

The study will be conducted without accessing protected health information (PHI). We will NOT seek access to any medical records.

7.3.2 ENROLLMENT/BASELINE

Following recruitment screening via telephone, interested individuals will schedule and attend an enrollment visit at which they will provide informed consent and be further assessed for eligibility, which includes assessment of self-reported inclusion/exclusion criteria (including appropriate level of suicide risk on the SITBI-- see information in section 5.1). If ineligible, they will be referred back to their mental health provider and receive payment for the enrollment visit. If eligibility is confirmed, they will be further characterized using the SCID-I and SCID-II and complete various psychosocial questionnaires. In addition, they will be trained in the protocol for urine ovulation testing, daily telephone assessments, and the patch/pill administration schedule. Participants will be randomized to one of six possible condition orders at that time.

The study agent will not be administered until Lab assessment 1 (i.e., not at this enrollment visit).

7.3.3 FOLLOW-UP

Following the baseline/enrollment visit, participants will remain in contact with study staff and will begin ovulation testing as instructed. When ovulation testing is positive (day 0), the participant will contact the study staff to schedule the first three laboratory assessment visits (visits for condition 1) on days +7, +14, and +22. All laboratory assessment visits are identical in structure and content, with the singular exception that the first laboratory visit of each condition will include: (1) a pregnancy test that must be negative prior to dispensing study medication, (2) a urine drug screen, and (3) assessment of height and weight (BMI). Between conditions, participants will again remain in contact with study staff to schedule ovulation testing in the next menstrual cycle. Once again, when ovulation is confirmed (day 0), the final 3 laboratory assessments (for condition 2) will be scheduled on days +7, +14, and +22. These visits may be scheduled up to +/-2 days in either direction.

Variable	Interview Measure	Self-Report Measure	Task Measure					
Vitals (first lab of each condition)	-	-	Height/Weight					
Urine Pregnancy Screen (first lab of each condition)	-	-	x					
Urine Drug Screen (first lab of each condition)	x	Х	x					
Blood Sample (48 ml)	-	-	E2/P4/ALLO/Inflammatory Gene Expression					
Suicidality	Full SITBI	-	-					
Depression	-	CESD	-					
Hopelessness	-	BHI	FT-IRAP					
Inhibitory Control	-	UPPS-P	SST					
Threat Sensitivity	-	STAI	DPT					
Negative Social Appraisals	-	SSES	SAR-IAT					
Side Effects, AEs, and Compliance Monitoring	Х	-	-					
Parasympathetic Activity	-	-	Respiratory Sinus Arrhythmia					

• Follow-Up Assessments Administered (see section 4.1 for Abbreviations):

Follow-Up Timeline:

Condition 1 (Follow-Up Visits 1-3):

- Ovulation Testing

- Positive Ovulation Test #1= Day 0

- Study Followup Visits 1-3 Scheduled for days +7, +14, +22

- Study Followup Visit 1 (Day +7): Assessments, pregnancy test, drug test, vitals, administration of study agent patch A and dispensation of pills (Condition 1)

- Study Followup Visit 2 (Day +14): Assessments, replacement of study agent patch A with patch B (Condition 1)

- Removal of study patch and end of pills on day +21

- Study Followup Visit 3 (Day +22): Assessments

CLEAR 2 Study Protocol: Hormones and Suicide Risk, Version 9, 07-02-2020, Page 33 of 64

Condition 2 (Follow-Up Visits 4-6):

- Ovulation Testing
- Positive Ovulation Test #2= Day 0
- Study Followup Visits 4-6 Scheduled for days +7, +14, +22

- Study Followup Visit 4 (Day +7): Assessments, pregnancy test, drug test, vitals, administration of study agent patch A and dispensation of pills (Condition 2)

- Study Followup Visit 5 (Day +14): Assessments, replacement of study agent patch A with patch B (Condition 2)

- Removal of study patch and end of pills on day +21

- Study Followup Visit 6 (Day +22): Assessments

Condition 3 (Follow-Up Visits 7-9):

- Ovulation Testing
- Positive Ovulation Test #2= Day 0
- Study Followup Visits 4-6 Scheduled for days +7, +14, +22

- Study Followup Visit 4 (Day +7): Assessments, pregnancy test, drug test, vitals, administration of study agent patch A and dispensation of pills (Condition 3)

- Study Followup Visit 5 (Day +14): Assessments, replacement of study agent patch A with patch B (Condition 3)
- Removal of study patch and end of pills on day +21
- Study Followup Visit 9 (Day +22): Assessments, Schedule Debriefing

7.3.4 FINAL STUDY VISIT

Debriefing visits will be scheduled within 15 days of study completion. In this final visit, a final risk assessment will be conducted and the participant will be referred as appropriate for additional clinical care. This final risk evaluation visit is included in order to reduce the likelihood of emergent risk following withdrawal from exogenous hormones in participants who had the placebo-experimental condition order. Participants will not be provided with individualized study results.

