7.3.5 EARLY TERMINATION VISIT

Should early termination be deemed necessary (following procedures detailed above), and the situation does not involve a need for immediate hospitalization of the participant, then the participant will be invited to an early termination visit in which the full typical debriefing interview (i.e., risk assessment and referral as appropriate) will be conducted.

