7.3.7 SCHEDULE OF EVENTS TABLE

Procedures	Screening	Enrollment/Baseline	IDS RANDOMIZATION	Follow-Up (Condition 1, Visit 1)	Follow-Up (Condition 1, Visit 2)	Follow-Up (Condition 1, Visit 3)	Follow-Up (Condition 2, Visit 4)*	Follow-Up (Condition 2, Visit 5)*	Follow-Up (Condition 2, Visit 6)*	Final Visit/ Debriefing Visit
Informed Consent	Verbal	Written								
	х	х								
Demographics	х	х								
Medical History/Inclusion/Exclusion Criteria	х	х								
SCID – Diagnostic Interview		Х								
SITBI – Suicidality Interview		Х	Х	Х	Х	Х	Х	Х	Х	Х
Randomization			Х							
Administer Study Agent E2 (or placebo) Patch				х	х		Х	х		
Dispense Study Agent P4 (or placebo) Pills				Х	Х		Х	Х		
Height/Weight				Х			Х			
Pregnancy and Drug Tests				Х			Х			
E2/P4/ALLO/Inflammatory Gene Expression Blood Measure				х	х	х	х	х	х	
CESD - Depression Self-Report				Х	Х	Х	Х	Х	Х	
BHI – Hopelessness Self-Report				Х	Х	Х	Х	Х	Х	
STAI – Anxiety/Threat Sensitivity Self-Report				х	Х	х	Х	Х	Х	
SSES – Negative Social Appraisals Self-Report				х	х	х	х	х	х	
UPPS-P – Impulsivity/Inhibitory Control Self-Report				х	Х	х	Х	Х	Х	
FT-IRAP – Hopelessness Task				х	х	х	Х	х	х	
SAR-IAT – Negative Social Appraisal Task				х	Х	х	Х	Х	Х	
SST – Inhibitory Control Task				Х	Х	Х	Х	Х	Х	
DPT – Threat Sensitivity Task				Х	Х	Х	Х	Х	Х	
Adverse Event/Side Effect Evaluation				Х	Х	Х	Х	Х	Х	
Parasympathetic Activity – Respiratory Sinus Arrythmia				Х	Х	Х	Х	Х	Х	

*Condition 3, Visits 7-9 are identical to Condition 2, Visits 4-6.

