8 ASSESSMENT OF SAFETY

The safety of the study and its participants (as described in 2.3.1) will be monitored via (1) Supervising physician [name]./Ph.D. (hormone-related AEs) and [name]. (mood and suicide-related AEs) as well as (2) a Data and Safety Monitoring Board (DSMB).

AEs will be assessed daily during the telephone contacts in the two administration conditions, and will be assessed weekly at laboratory visits. All AEs will be reported immediately to the PI and [name], who will determine severity and next steps.

A DSMB of three experts outside the PI's department will evaluate AEs that are submitted during scheduled reviews (every 6 months). The DSMB will be composed of MDs and PhDs from relevant disciplines, including clinical psychology, gynecology, and endocrinology.

Although not expected given the doses and duration of hormone exposure, the DSMB will, during scheduled reviews, specifically evaluate the frequency of AEs related to the hormonal RCT. The DSMB will specify the tables and data it wishes to have presented to it at all meetings, including but not limited to, moderate to severe side effects and all serious adverse events. **DSMB review of this study will occur every six months**. At these meetings the DSMB will also review data from participants who have been discontinued by study staff or who have withdrawn or dropped out of the study, and the reasons for discontinuation. The DSMB will also identify if any study procedures should be altered or stopped in the event of an indication of harm to participants attributable to the study interventions. The DSMB will evaluate issues of participant safety as well as the adequacy and integrity of accumulating data, review of enrollment data, and making recommendations regarding safety.

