8.3 TIME PERIOD AND FREQUENCY FOR EVENT ASSESSMENT AND FOLLOW-UP

The occurrence of an AE or SAE may come to the attention of study personnel during study visits and interviews of a study participant. All AEs including local and systemic reactions not meeting the criteria for SAEs will be captured on the appropriate documentation. Information to be collected includes event description, time of onset, clinician's assessment of severity, relationship to study product (assessed only by those with the training and authority to make a diagnosis), and time of resolution/stabilization of the event. All AEs occurring while on study must be documented appropriately regardless of relationship. All AEs will be followed to adequate resolution.

Pre-existing medical conditions are exclusionary for participation in the trial, with the exception of psychiatric conditions. Any psychiatric condition or symptom that is present at the time that the participant is screened, including mood symptoms and suicidal *ideation*, will be considered as baseline and not reported as an AE. However, if the study participant's condition or symptom deteriorates significantly with regard to the severity or impact of the symptom on the participants functioning or safety (as determined by Drs. [name] and [name]) at any time during the study, it will be recorded as an AE. UPs will be recorded in the data collection system throughout the study.

Changes in the severity of an AE will be documented to allow an assessment of the duration of the event at each level of severity to be performed. AEs characterized as intermittent require documentation of onset and duration of each episode.

The PI will record all reportable events with start dates occurring any time after informed consent is obtained until 7 (for non-serious AEs) or 30 days (for SAEs) after the last day of study participation. At each phone call and study visit, study staff will inquire about the occurrence of AE/SAEs since the last visit. All AEs will be immediately reported to the PI, who will respond (psychiatric AEs) or consult with [name] as soon as possible (for medical AEs). Events will be followed for outcome information until resolution or stabilization.

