8.4 REPORTING PROCEDURES

8.4.1 ADVERSE EVENT REPORTING

Study staff will screen for all AEs at each telephone call and study visit. [name] will be on call for all visits and telephone calls to ensure that emergent mood deterioration or suicide risk can be immediately handled by a licensed clinical psychologist with experience in suicide risk assessment ([name]) using the LRAP/UWRAP protocol (the tool recommended by NIH for clinical trials with suicidal subjects). Medical/physical AEs will be discussed as soon as possible with [name].

The PI [name] (in consultation with [name]) will review all protocol data at monthly meetings, including enrollment and retention statistics and aggregate reports of side effects/AEs. As the contact PI, [name] will be the one responsible for reporting any severe AEs to the IRB and DSMB within 1 week. Since we are employing a marketed pharmaceutical product (i.e., a non-IND study), unexpected Serious AEs will be also be reported to the FDA Medwatch Program. The NIMH program officer will be notified of any study modifications or suspension imposed by the DSMB or local IRB in response to an AE.

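### The 30-day SAE window has no scheduled contact after the debriefing visit, and the sections disagree on whether AEs are asked about at that visit

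*Combined protocol and SAP*

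**What the plan says.** **Recording window.** Section 8.3 has the PI record events from consent "until 7 (for non-serious AEs) or 30 days (for SAEs) after the last day of study participation". The documents do not define that last day.

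**When staff ask.** Section 8.3 states: "At each phone call and study visit, study staff will inquire about the occurrence of AE/SAEs since the last visit". Section 8.4.1 repeats the rule: "Study staff will screen for all AEs at each telephone call and study visit". Section 8 is narrower: "AEs will be assessed daily during the telephone contacts in the two administration conditions, and will be assessed weekly at laboratory visits". The trial has three conditions, not two.

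**What the closing visits contain.** Section 7.3.4 says of debriefing: "In this final visit, a final risk assessment will be conducted and the participant will be referred as appropriate for additional clinical care". The debriefing table in 7.1.1 lists the full SITBI and nothing else. At early termination (7.3.5), "the full typical debriefing interview (i.e., risk assessment and referral as appropriate) will be conducted". In the schedule of events (7.3.7), the row "Adverse Event/Side Effect Evaluation" is marked for the laboratory visits and is blank under the final visit.

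**Other routes to an event.** Section 7.3.6 rules out unscheduled visits. Section 7.3.1 states: "We will NOT seek access to any medical records". No contact of any kind is listed after debriefing.

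**The concern.** A recording window finds events only if someone looks during it or asks about it afterwards. Here the window outlasts every planned contact, and there is no record search to stand in for one.

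The protocol itself names venous thromboembolism and suicide attempt as its notable SAEs (5.5, 8.1.2), and 7.3.4 justifies the debriefing visit by risk that may emerge after exogenous hormones stop. In a trial of 60 enrolled women, SAE counts will be small, so one missed event can change the safety picture given to the DSMB or reported at the end.

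The conflict between sections is a practical matter too. Staff working from the schedule or the debriefing table would carry out the SITBI but might not ask about, say, a thrombosis. Staff working from 8.3 would ask.

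**Working it through.** The plan gives no figure to reproduce. The check sets the sections side by side and counts days, with day 0 the positive ovulation test in the third condition.

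**Inputs**
- Study agent ends on day +21; Visit 9 is on day +22, plus or minus 2 days (7.3.3).
- Phone measures end 5 days after the last patch or pill (4.1).
- Debriefing is within 15 days of study completion (7.3.4). Section 7.1.1 instead counts 15 days from the end of the second condition, which does not fit a three-condition trial. I take study completion to mean Visit 9.
- The window is 30 days for SAEs and 7 days for non-serious AEs (8.3).
- Participation lasts 6 to 7 months (Protocol Summary), taken as 182 to 213 days.
- There are six condition orders (7.3.2, 10.6.1), 60 women enrolled and 40 intended completers (10.5).

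**Timeline after the last dose**
1. Visit 9, day +22: AE evaluation is marked.
2. Phone measures run to day 21 + 5 = +26. Section 4.1 ties the daily safety call to active condition days, so AE questions on days +22 to +26 are likely but not certain.
3. From about day +27 to debriefing there is no contact. The latest debriefing is day 22 + 15 = +37, so this gap is up to about 11 days. The since-last-visit inquiry in 8.3 covers it, if it is carried out at debriefing.
4. Debriefing includes the full SITBI, which has suicide-attempt items. It does not ask about thromboembolism.
5. After debriefing: no scheduled contact.

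**Length of the stretch without contact**
- If debriefing is the last day of participation, the SAE window runs to day 37 + 30 = +67 at the latest. All 30 days follow the last contact, as do all 7 days of the AE window.
- If Visit 9 is the last day, the SAE window ends on day 22 + 30 = +52. With debriefing on day +37, 52 − 37 = 15 days remain. An earlier debriefing leaves more. The AE window would end on day 22 + 7 = +29, and the calls cover part of it.

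**Share of SAEs under an assumed flat daily hazard**

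Share = days without contact / (participation days + 30).

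| Last day of participation | 182 days | 213 days |
|---|---|---|
| Debriefing | 30/212 = 14.2% | 30/243 = 12.3% |
| Visit 9, debriefing 15 days later | 15/212 = 7.1% | 15/243 = 6.2% |

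**Women whose last condition is active.** Four of the six orders end in B or C. Assuming equal allocation across orders, 40 × 4/6 = 26.7, or about 27 of the 40 completers.

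**The case against.** **The final visit does include AE inquiry.** A reader of the schedule might infer that it has none. Sections 8.3 and 8.4.1 both say otherwise, and debriefing is a study visit. The blank cell is also weak evidence by itself: the same table leaves the enrollment column blank for questionnaires that 7.1.1 lists there. This stands. The defect at the closing visits is a conflict between sections, not a proven absence. It still needs resolving, because the debriefing table and both visit descriptions point the same way as the blank cell.

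**Events after the last hormone withdrawal are actively sought.** A reader might infer that everything after day +21 depends on volunteered reports. The documents do not support that. Visit 9, the phone measures to about day +26 and the debriefing SITBI cover part of the period. Section 6.1.8 also has women discontinued by the PI followed until resolution. That is follow-up of a known problem, not a scheduled question about new SAEs, and it does not reach women who leave by choice. The early termination visit is by invitation and is not planned for those needing immediate hospitalisation.

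**The consequences are limited.** The halting rule (5.5, 8.5, 10.4.7.1) counts events with onset during patches or pills, and 10.4.4 codes AEs by emergence in the treatment timeframe. Events after debriefing enter neither. Order is randomised over all six permutations, so each condition can come last, and no between-condition bias follows. Both points stand. What remains is the completeness of the SAE record, which the DSMB reviews under section 8.

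**A recording window does not promise active solicitation.** This is fair as a reading of 8.3. The protocol should then say that capture after debriefing is passive. As written, a reader of the final report would assume 30 days of SAE follow-up that nobody carried out.

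**Conclusion.** The point holds in this form: SAEs that start after debriefing and within the stated window are seen only if volunteered, and the sections on AE inquiry at the closing visits must be reconciled.

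The stretch without contact is 30 days or at least about 15 days, depending on the undefined last day of participation. No reading brings it to zero. The corresponding 6% to 14% of SAEs assumes a flat hazard, which the documents neither state nor support. If risk concentrates in the days just after withdrawal, much of it falls where Visit 9 and the calls still look, so the share could be lower; later-onset events would raise it.

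It is tempting to apply the four-in-six fraction to all 60 enrolled women and say that 40 end on active hormone. Only women who reach the third condition end on it, so about 27 of 40 completers is the supportable figure, given equal allocation. No bias between conditions and no effect on the halting rule is shown.

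This is worth changing because the remedy is cheap and lets the protocol deliver its own stated window. It does not threaten the primary analysis.

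**What to change.** 1. Mark the AE/SAE inquiry at the debriefing and early termination visits: in the debriefing table of 7.1.1, in 7.3.4 and 7.3.5, and in the final-visit column of 7.3.7.
2. Define the last day of study participation, and make the debriefing timing in 7.1.1 agree with 7.3.4.
3. Add one scripted AE/SAE phone contact at the end of the 30-day window for every randomised woman, including those who leave early.
4. Align section 8 with 8.3 and 8.4.1, including its count of two conditions.

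The cost is a few questions at existing visits and about 60 short calls by staff who already make daily calls. Follow-up per woman becomes slightly longer, and the reported SAE count may rise slightly. If the call is not adopted, the protocol and the final report should state that SAE capture after debriefing is passive.
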